### **Intervention groups and duration:**

Participants will be randomly assigned (1:1) to either Arm A (experimental) or Arm B (control):

- Arm A: Amcnestrant (SAR439859) 200 mg + tamoxifen-matching placebo
- Arm B: Amcnestrant (SAR439859)-matching placebo + tamoxifen 20 mg

Treatments in both arms are given orally.

Participants will receive their assigned treatment for the planned duration of 5 calendar years or until the occurrence of any withdrawal criterion, whichever occurs first.

During the treatment period, men and pre/perimenopausal women will receive GnRH analogs as approved in the respective countries.

No dose reductions for amcnestrant and tamoxifen are permitted but dosing omissions are allowed in case of toxicity. Temporary study treatment interruption is also permitted in special circumstances as described in protocol [Section 6.5.3](#).

### Study intervention(s)

#### *Investigational medicinal products (IMPs)*

#### **Amcnestrant (SAR439859) and amcnestrant (SAR439859)-matching placebo**

- Amcnestrant formulation: 200 mg tablets
- Route of administration: oral route
- Dose regimen: the recommended dose is 200 mg once daily, to be taken approximately at the same time each day, with food.
- Amcnestrant-matching placebo will be supplied as tablets identical to amcnestrant 200 mg tablets in appearance.

#### **Tamoxifen and tamoxifen-matching placebo**

- Tamoxifen formulation: 20 mg tablets
- Route of administration: oral route
- Dose regimen: the recommended dose is 20 mg once daily, to be taken approximately at the same time each day, with food.
- Tamoxifen-matching placebo will be supplied as tablets identical to tamoxifen 20 mg tablets in appearance.

For IMPs, if a dose is vomited or omitted the participant should not take the dose later or 2 doses at the next planned dose.

### *Non-investigational medicinal products (NIMPs)*

- Goserelin or other GnRH analog approved for use in early breast cancer as per site/country availability.

### **Statistical considerations**

#### **Sample size determination:**

For IBCFS primary endpoint, a total of 568 IBCFS events will be needed to reject the null hypothesis using a log-rank test at the one-sided level of 2.5% and 90% power under the assumption of a hazard ratio (HR) of 0.76. Assuming proportional hazards under an exponential model and based on an anticipated 4-year IBCFS rate of 82% in the tamoxifen arm, this is expected to correspond to a 4-year IBCFS rate of 86% in the amcenestrant arm.

Based on piecewise enrollment assumption over 24-month period, an IBCFS cut-off date (COD) of 60 months after the first participant randomized and an annual dropout rate of 1%, a total of 3738 participants are expected to be randomized in a 1:1 ratio into the amcenestrant and tamoxifen arms.

The number of events/sample size calculation accounts for two interim analyses at 1/3 (non-binding futility only) and 3/4 (efficacy and non-binding futility) of the planned total number of events.

#### **Main analysis population:**

- Intent-to-treat (ITT) population: All participants who signed the informed consent form (ICF) and for whom there is a confirmation of successful allocation of a randomization number by IRT. Participants will be analyzed according to the treatment arm assigned at randomization. This is the primary population for all efficacy parameters.
- Safety population: All participants who signed the ICF and for whom there is a confirmation of successful allocation of a randomization number by IRT and who took at least 1 dose of study intervention. Participants will be analyzed according to the treatment arm they actually received. This population is the primary population for the analysis of all safety parameters.

#### **Analysis of primary endpoint:**

Primary efficacy analysis will consist of IBCFS comparison between the amcenestrant arm and the tamoxifen arm through a logrank test procedure stratified by the stratification factors (except geographic region to minimize the risk of power loss due to large number of strata and potentially low number of events in some strata) as entered in the IRT. A one-sided Type I error rate of 2.5% will be used for statistical testing.

The HR estimates and corresponding confidence intervals will be provided using the Cox proportional hazard model stratified by the same stratification factors as those used for the logrank test described above. The IBCFS quantiles and IBCFS rates at different time points (calculated using the Kaplan-Meier methods) as well as corresponding 95% CIs will be presented by treatment arm. The Kaplan-Meier IBCFS curves will also be provided.

## **Analysis of main secondary endpoints:**

### Key secondary endpoint (IDFS)

Same statistical methods as defined for the IBCFS will be used. To ensure a strong control of the overall Type I error rate at a one-sided 2.5%, a hierarchical testing strategy will be used. In other words, comparison between arms on the IDFS will be performed only if the primary analysis of the IBCFS is statistically significant.

### Other secondary efficacy endpoints

For the following time to event secondary endpoints (DRFS, LRRFS, OS), same statistical methods as defined for the IBCFS and IDFS endpoints will be used, with the exception that no statistical testing will be performed.

[figure not shown]
For the endpoint BCSS, the HR estimate and corresponding 95% two-sided confidence intervals (CIs) will be provided by using Fine and Gray model accounting for competing risks and stratified by the stratification factors (except geographic region) as entered in the IRT. The cumulative incidence of breast cancer-related deaths at different timepoints (calculated using the cumulative incidence function method) as well as 95%CIs will be presented by treatment arm. The corresponding BCSS rates and 95%CIs will be computed as “1 minus cumulative incidence function”. The cumulative incidence curves will also be provided.

### Analysis of safety endpoints

Adverse events will be coded according to MedDRA and graded according to the NCI-CTCAE v5.0. Summaries will be provided for all grades combined and for Grade  $\geq 3$  (including Grade 5). Adverse event incidence table will be provided by treatment group for all types of treatment-emergent adverse events (TEAEs): all TEAEs, all treatment emergent AESI (defined with a PT or a prespecified grouping), all treatment emergent SAEs, all TEAEs related to IMP, all TEAEs leading to permanent treatment discontinuation and all TEAEs leading to dose modification. Death will also be analyzed.

Hematology and clinical chemistry results will be graded according to the NCI-CTCAE v5.0, when applicable. Number and percentage of participants with laboratory abnormalities (all grades and by grade) using the worst grade during the on-treatment period will be provided on the safety population.

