**Table 1 - Risk assessment**

Potential risk of clinical significance	Summary of data/rationale for risk	Mitigation strategy
Study intervention Amcenestrant (SAR439859)		
Gastrointestinal toxicity	
AMEERA-1 Arm#1 (Parts A and B): A total of 22 out of 62 patients who received amcenestrant monotherapy (>20 mg QD) developed various GI toxicities considered to be related to amcenestrant, none of them were of Grade <math>\geq 3</math>.
 
AMEERA-1 Arm#2 (Parts C and D): A total of 19 out of 39 patients who received 200 mg amcenestrant and palbociclib developed GI toxicities considered to be associated to amcenestrant, none of them were of Grade <math>\geq 3</math>.
 
In studies conducted in healthy subjects, there were few single occurrences of GI events considered related to amcenestrant. None of them were of Grade <math>\geq 3</math>
	
Events <math>\geq</math> Grade 3 are to be closely monitored.
 
Preventive or corrective treatment(s): antiemetics, antidiarrheal.

Hepatotoxicity	
Preclinical safety data have shown evidence of hepatotoxicity in repeat dose toxicity study at 100 mg/kg/day in dogs.
 
AMEERA-1 Arm#1 (Parts A and B) / Arm#2 (Parts C and D): No event of hepatotoxicity considered to be related to amcenestrant has been reported.
 
Studies in healthy subjects: In completed or ongoing studies in healthy subjects, 3 subjects developed asymptomatic transient ALT increase <math>\geq 2 \times</math> ULN with amcenestrant 300 mg SD alone or in combination with rifampicin. All occurrences were Grade 1. All events of ALT increase were non serious and spontaneously resolute.
	
Monitor LFT in cases of increase of Grade <math>\geq 3</math> ALT, listed as AESI in the study.
 
Monitor patients with symptoms/signs suggestive of hepatotoxicity: jaundice, increase of liver function tests (LFT) (ALT, AST, GGT, ALP and bilirubin). Patients with impaired liver function should not be included in the study (exclusion criterion E 20).

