## Diagnostic assessments

E 17. Inadequate hematological function including:

- Hemoglobin <9 g/dL or blood transfusion support within 2 weeks prior to randomization
- Neutrophils <1.5 x 10^9/L or growth factor support within 2 weeks prior to randomization
- Platelet count <100 x 10^9/L or platelet transfusion support within 2 weeks prior to randomization

E 18. Inadequate renal function with estimated glomerular filtration rate (eGFR) <30 mL/min/1.73 m^2 as estimated using the Modification of Diet in Renal Disease (MDRD) formula.

E 19. Prothrombin time/international normalized ratio (INR) >1.5 times the upper limit of normal (ULN) or outside therapeutic range if receiving anticoagulation that would affect the prothrombin time/INR.

E 20. Inadequate liver function as defined as:

- Aspartate aminotransferase (AST) and/or alanine aminotransferase (ALT) >1.5 x ULN
- Alkaline phosphatase (ALP) >1.5 x ULN
- Total bilirubin >1.5 x ULN (>3.0 x ULN with direct bilirubin within normal range in patients with Gilbert's disease)

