### **9.2.5.2 Laboratory variables, vital signs and electrocardiograms (ECGs)**

#### **Analyses according to PCSA and NCI grading**

For laboratory variables, analyses according to NCI grading will be made based on NCI-CTCAE version 5.0. In addition, for laboratory variables for which NCI-CTCAE scale is not applicable, vital signs and ECG variables, PCSA analyses will be performed based on the PCSA list currently in effect at Sanofi at the time of the database lock.

Analyses according to PCSA and NCI grading will be performed based on the worst value during the treatment-emergent period, using all measurements (either local or central, either scheduled, nonscheduled or repeated).

For laboratory variables, vital signs and ECG variables, the incidence of participants with at least one PCSA during the treatment-emergent period will be summarized regardless of the baseline level and according to the following baseline status categories:

- Normal/missing
- Abnormal according to PCSA criterion or criteria

For laboratory variables graded by NCI-CTCAE.

- The number (%) of participants with abnormal laboratory tests at baseline will be presented by grade.
- The number (%) of participants with abnormal laboratory tests during the treatment-emergent period will be summarized by grade. When appropriate, the number (%) of participants with abnormality of any grade and with Grade 3-4 abnormalities will be provided.

For ECG, the incidence of participants with at least one abnormal ECG during the treatment-emergent period will be summarized regardless of the baseline level and according to the following baseline status categories:

- Normal/missing
- Abnormal

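### For CTCAE-graded laboratory tests, no planned table relates a participant's worst on-treatment grade to the baseline grade, which can dilute any-grade and Grade 1 contrasts between arms

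*Combined protocol and SAP*

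**What the plan says.** The synopsis (Analysis of safety endpoints) sets the rule for hematology and chemistry: "Number and percentage of participants with laboratory abnormalities (all grades and by grade) using the worst grade during the on-treatment period will be provided", in the safety population.

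Section 9.2.5.2 says the same in more detail. The basis is common to all variables: "Analyses according to PCSA and NCI grading will be performed based on the worst value during the treatment-emergent period, using all measurements". For CTCAE-graded tests two tables follow. The first is for baseline: "The number (%) of participants with abnormal laboratory tests at baseline will be presented by grade". The second is for treatment: "The number (%) of participants with abnormal laboratory tests during the treatment-emergent period will be summarized by grade". The section names no rule or table that connects them within a participant.

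The other variables are handled differently. The scope is given as "for laboratory variables for which NCI-CTCAE scale is not applicable, vital signs and ECG variables, PCSA analyses will be performed", and for these the incidence of at least one abnormality "will be summarized regardless of the baseline level and according to the following baseline status categories", namely normal or missing versus abnormal.

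Eligibility leaves room for mild abnormality at entry. Exclusion criterion E 20 begins at "Aspartate aminotransferase (AST) and/or alanine aminotransferase (ALT) >1.5 x ULN", with the same multiple for alkaline phosphatase and bilirubin. E 17 excludes hemoglobin only below 9 g/dL.

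**The concern.** A table of worst grades cannot separate a value that was abnormal before the first dose from one that became abnormal on treatment. A separate baseline table shows the background in each arm but not which participants moved. The same protocol applies a stricter idea elsewhere: Section 9.2.5.1 counts an adverse event as treatment-emergent only if it arises, worsens or turns serious on treatment, and the PCSA variables are split by baseline status. Only the graded tests lack such a link.

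This matters mainly for low grades, because adverse event reporting does not fill the gap. Under Section 8.2.3 a laboratory value becomes an adverse event only if it leads to discontinuation or dose modification, is serious, or is an AESI. The ALT AESI in Section 8.3.6 starts at Grade 3. Table 14 calls for omission at Grade 2 ALT, so that change would be recorded, but it calls for no adjustment at Grade 1 ALT or at Grade 1-2 in other tests. Such changes would normally appear only in the laboratory tables. Hepatotoxicity is a listed potential risk, and of the ALT rises in healthy subjects Table 1 says: "All occurrences were Grade 1".

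**Working it through.** **The plan's own figures.** The only sizing is for efficacy: 568 events and 3738 participants. Both reproduce. With O'Brien-Fleming-type spending at 3/4 information, one-sided 2.5%, HR 0.76 and 90% power, 567.5 events are needed. The Table 12 accrual with 1% annual dropout gives 3736 participants for 568 events at month 60. The present point does not touch them. No figure is stated for laboratory safety. I take 3738/2 = 1869 per arm.

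**Inputs that the documents do not give (assumptions).** b is the share abnormal at entry who stay graded abnormal on treatment, equal in both arms by randomization. p0 and p1 are the rates of new abnormality among the rest.

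**Formulas.** The planned any-grade rate per arm is b + (1-b)p. The displayed difference is therefore (1-b)(p1-p0), and the displayed ratio is [b + (1-b)p1] / [b + (1-b)p0].

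**Worked case, b = 20%, 5% vs 7%.**
- Planned table: 0.20 + 0.80 x 0.05 = 24.0%, and 0.20 + 0.80 x 0.07 = 25.6%. Ratio 1.07. z = 0.016 / sqrt(2 x 0.248 x 0.752 / 1869) = 1.13.
- Among those normal at entry (0.80 x 1869 = 1495 per arm): 5% vs 7%, ratio 1.40, z = 0.02 / sqrt(2 x 0.06 x 0.94 / 1495) = 2.30.
- Worse than baseline over all 1869, if nobody abnormal at entry worsens: 4.0% vs 5.6%, z = 0.016 / sqrt(2 x 0.048 x 0.952 / 1869) = 2.29. The gain does not depend on restricting the denominator.

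**Range for 5% vs 7%.** The last two columns give the chance of a nominal two-sided p < 0.05. They are a yardstick only, because no laboratory test is planned.

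| b | Planned table | Displayed ratio | As planned | Normal at entry |
|---|---|---|---|---|
| 0% | 5.0% vs 7.0% | 1.40 | 73% | 73% |
| 2% | 6.9% vs 8.9% | 1.28 | 60% | 72% |
| 10% | 14.5% vs 16.3% | 1.12 | 33% | 69% |
| 20% | 24.0% vs 25.6% | 1.07 | 20% | 63% |
| 30% | 33.5% vs 34.9% | 1.04 | 15% | 58% |

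**Other contrasts (as planned versus normal at entry).**
- 10% vs 13%: 54% vs 78% at b = 10%; 26% vs 67% at b = 30%.
- 20% vs 24%: 67% vs 80% at b = 10%; 41% vs 70% at b = 30%.
- 5% vs 10% at b = 20%: the table reads 24.0% vs 28.0%, ratio 1.17 instead of 2.00. Even so, z = 0.04 / sqrt(2 x 0.26 x 0.74 / 1869) = 2.79, about an 80% chance, so a large effect would still show.

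**Partial persistence.** If 20% are abnormal at entry but only half stay so, and the other half are never counted, the 5% vs 7% case gives 0.10 + 0.80 x 0.05 = 14.0% and 0.10 + 0.80 x 0.07 = 15.6%, ratio 1.11. The dilution is smaller but present.

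**The case against.** **Section 9.2 is a summary.** It leaves technical detail to a SAP due before the first database lock, and a shift table is routine SAP content. Nothing in the text rules one out. This stands as a limit: if the SAP already contains that table, the point is closed. But Section 9.2.5.2 sets out these tables specifically, gives a baseline split for one class of variable, and gives none for the other.

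**The grading may already use baseline.** The protocol cites CTCAE v5.0 without reproducing it. If liver tests are graded relative to an abnormal baseline, an unchanged entry value would not count and the liver part of the argument would largely fall away. This stands: the documents do not settle it, so the liver case is conditional.

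**The quantities are assumed.** No entry prevalence or onset rate is given. E 20 admits only a narrow band above normal, and Table 1 names no hematological risk for either drug. This stands too, and is why a range starting at zero is shown.

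**Much is already visible.** Baseline grades are tabulated, a move from Grade 1 to Grade 2 appears in the Grade 2 row, Grade 3 or higher ALT is an AESI with expedited reporting, and the IDMC reviews cumulative safety. All true. None of it shows how many participants went from normal to Grade 1.

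**Conclusion.** The point holds for NCI-CTCAE-graded tests only. As written, the plan counts the worst grade for everyone and has no within-participant comparison with baseline. Any-grade and Grade 1 differences are multiplied by (1-b) on top of a background common to both arms. The loss is nil with no entry abnormalities and considerable for small effects at b of 10% to 30%. It rests on assumed prevalence, onset and persistence, and on permitted entry values being graded as abnormal.

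A reader might infer three stronger things that the documents do not support:
- That laboratory tables in general ignore baseline. The PCSA laboratory variables are split by baseline status.
- That the tables favour amcenestrant or would hide serious liver toxicity. Randomization gives both arms the same expected background, so this is attenuation and not directional bias, and Grade 3-4 counts are little affected.
- That the trial loses a definite amount of power. The laboratory summaries are descriptive.

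The severity is minor: safety reporting only, with no effect on efficacy analyses or monitoring rules.

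**What to change.** In Section 9.2.5.2 and the SAP, keep the planned worst-grade table and add two displays per arm for each CTCAE-graded test:
1. a shift table of baseline grade by worst on-treatment grade;
2. the number and percentage of participants whose worst on-treatment grade is higher than their baseline grade.

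Show participants with missing baseline separately. State in one sentence whether the grading of each liver test takes an abnormal baseline into account. Refer to the added displays in the synopsis. This brings the graded tests into line with the baseline split already used for PCSA variables.

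The cost is a few sentences and a little programming. Screening laboratory values are already scheduled for every participant, so no procedure, visit or sample size changes.

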**Data Monitoring/Other committee: Yes**

AI = aromatase inhibitor; C = Cycle; CT = chemotherapy; D = day; EOT = End of Treatment; IMP = investigational medicinal product; PO = per os; QD = once a day; R = randomization  
A cycle is defined as a 28-day period.

### 1.3 SCHEDULE OF ACTIVITIES (SOA)

Procedure	Screening Period	Treatment Period [5 years – C1-C65]					EOT	Follow-up Period	Notes
		0	1	2	3	4-10 Q12 weeks			
Patient Visit #	Baseline	C1 D1	C2 D1	C4 D1	C7, C10, C13, C16, C19, C22, C25 D1	C28, C34, C40, C46, C52, C58 D1	D30 after last IMP dose	Q12 months after last IMP dose	
Patient Cycle Visit #	Up to 28 days before randomization	±3	±3	±7	±7	±7	±7	±45	
Time Window (day)									
Inclusion exclusion criteria / Informed consent	X								Informed consent (including genetic sampling) may be signed prior to D-28. Recheck clinical status before randomization and/or first dose of study medication. For patients still on AI at screening, inclusion/exclusion criteria should be evaluated when AI has been discontinued
Demography, medical/surgical and disease history, prior cancer therapies	X								At screening visit only. Prior AI treatments (duration of treatment, reason(s) for discontinuation) to be collected. For patients still on AI at screening, medical history should be evaluated when AI has been discontinued.

Procedure	Screening Period	Treatment Period [5 years – C1-C65]					EOT	Follow-up Period	Notes
		0	1	2	3	4-10 Q12 weeks			
Patient Visit #	Baseline	C1 D1	C2 D1	C4 D1	C7, C10, C13, C16, C19, C22, C25 D1	C28, C34, C40, C46, C52, C58 D1	D30 after last IMP dose	Q12 months after last IMP dose	
Patient Cycle Visit #	Up to 28 days before randomization	±3	±3	±7	±7	±7	±7	±45	
Time Window (day)									
Vital signs, physical examination/ signs and symptoms	X	X a			X b		X	X	a. Visit 1 b. At visit 3 and then at each visit during the treatment period. Vital signs will be collected at baseline and during the treatment period.
ECOG performance status, body weight and height	X				X				Height will be collected at screening only. At baseline after patient has discontinued AI
Gynecological examination					X				From one year after randomization and annually until the end of treatment
Follicle-stimulating hormone (pre/perimenopausal women only)- Local labs	X								At screening for eligibility and to confirm the menopausal status. As per local regulations, to demonstrate postmenopausal status, serial measurements of FSH may be required.

Procedure	Screening Period	Treatment Period [5 years – C1-C65]					EOT	Follow-up Period	Notes
		0	1	2	3	4-10 Q12 weeks			
Patient Visit #	Baseline	C1 D1	C2 D1	C4 D1	C7, C10, C13, C16, C19, C22, C25 D1	C28, C34, C40, C46, C52, C58 D1	D30 after last IMP dose	Q12 months after last IMP dose	
Patient Cycle Visit #	Up to 28 days before randomization	±3	±3	±7	±7	±7	±7	±45	
Time Window (day)									
Estradiol (pre/perimenopausal women only) – Local labs	X a				X b				
a. At screening for eligibility and to confirm the menopausal status
 
b. At each visit during the treatment period, and at EOT.
 
Female participant will be categorized as premenopausal or postmenopausal at the time of study entry. This designation shall not change during the course of study participation; even if a premenopausal woman will become postmenopausal during the course of study participation, she will still be categorized as premenopausal for the purposes of the study.

Procedure	Screening Period	Treatment Period [5 years – C1-C65]					EOT	Follow-up Period	Notes
		0	1	2	3	4-10 Q12 weeks			
Patient Visit #	Baseline	C1 D1	C2 D1	C4 D1	C7, C10, C13, C16, C19, C22, C25 D1	C28, C34, C40, C46, C52, C58 D1	D30 after last IMP dose	Q12 months after last IMP dose	
Patient Cycle Visit #	Up to 28 days before randomization	±3	±3	±7	±7	±7	±7	±45	
Time Window (day)									
Pregnancy test (pre/perimenopausal women only) – Local labs	X a				X b				
a. Serum pregnancy test (β-hCG) to be done within 14 days before starting study treatment.
 
b. Urine pregnancy test (dipstick) to be done for WOCBP:
 
 
- At each visit from visit 1 to visit 10
 
- Every 12 weeks from visit 11 until the end of the mandatory period of contraception as per Appendix 4: either onsite or at home
 

Procedure	Screening Period	Treatment Period [5 years – C1-C65]					EOT	Follow-up Period	Notes
		1	2	3	4-10 Q12 weeks	11-16 Q24 weeks			
Patient Visit #	0	1	2	3	4-10 Q12 weeks	11-16 Q24 weeks	17	≥18	
Patient Cycle Visit #	Baseline	C1 D1	C2 D1	C4 D1	C7, C10, C13, C16, C19, C22, C25 D1	C28, C34, C40, C46, C52, C58 D1	D30 after last IMP dose	Q12 months after last IMP dose	
Time Window (day)	Up to 28 days before randomization	±3	±3	±7	±7	±7	±7	±45	
Laboratory assessments – Local labs	X a				X b				Hematology, biochemistry panels and coagulation: a. To be performed at screening within 7 days of Cycle 1 D1 after patient has discontinued AI. b. At each visit during the treatment period, at EOT, and as clinically indicated.  Lipids assessments on Visit 1, Visit 3, Visit 4, and as clinically indicated.

Procedure	Screening Period	Treatment Period [5 years – C1-C65]					EOT	Follow-up Period	Notes
		1	2	3	4-10 Q12 weeks	11-16 Q24 weeks			
Patient Visit #	0	1	2	3	4-10 Q12 weeks	11-16 Q24 weeks	17	≥18	
Patient Cycle Visit #	Baseline	C1 D1	C2 D1	C4 D1	C7, C10, C13, C16, C19, C22, C25 D1	C28, C34, C40, C46, C52, C58 D1	D30 after last IMP dose	Q12 months after last IMP dose	
Time Window (day)	Up to 28 days before randomization	±3	±3	±7	±7	±7	±7	±45	
Bone mineral densitometry ) / Dual-energy X-ray absorptiometry (DXA)	X a				X b				a. Screening: to be done if not already done in the past 12 months prior to randomization. b. Post baseline: every 2 years from randomization (+/-1 month) until end of follow -up period Other quantitative methods giving similar T-score values, including ultrasound bone densitometry and QCT (quantitative computerized tomodensitometry) are also accepted.
Bone Turnover Markers (CTX, P1NP) – Local labs	X a				X b				a. Screening: to be done if not already done in the past 12 months prior to randomization. b. During the treatment period: every 2 years from randomization (+/-1 month)
12-lead ECG	X						X		Screening (after patient has discontinued AI), EOT and as clinically indicated

Procedure	Screening Period	Treatment Period [5 years – C1-C65]					EOT	Follow-up Period	Notes
		0	1	2	3	4-10 Q12 weeks			
Patient Visit #	Baseline	C1 D1	C2 D1	C4 D1	C7, C10, C13, C16, C19, C22, C25 D1	C28, C34, C40, C46, C52, C58 D1	D30 after last IMP dose	Q12 months after last IMP dose	
Patient Cycle Visit #	Up to 28 days before randomization	±3	±3	±7	±7	±7	±7	±45	
Time Window (day)	X								Eligibility criteria data collection and central confirmation of ER and PgR biomarkers to be completed prior to IRT randomization call
Randomization									
Study Treatment Administration:									
IMP dispensation call		X		X	X	X a			a. Visit 16 (C58): IMP dispensation from C58 to C65, ie, 32 weeks
amcenestrant + tamoxifen-matching placebo		Once daily ↔							
tamoxifen + amcenestrant-matching placebo		Once daily ↔							
NIMP: GnRH analog		↔							- Goserelin or other GnRH analog approved for use in early breast cancer as per site/ country availability - In men and pre/perimenopausal women

Procedure	Screening Period	Treatment Period [5 years – C1-C65]					EOT	Follow-up Period	Notes
		0	1	2	3	4-10 Q12 weeks			
Patient Visit #	Baseline	C1 D1	C2 D1	C4 D1	C7, C10, C13, C16, C19, C22, C25 D1	C28, C34, C40, C46, C52, C58 D1	D30 after last IMP dose	Q12 months after last IMP dose	
Patient Cycle Visit #	Up to 28 days before randomization	±3	±3	±7	±7	±7	±7	±45	
AE/SAE review	←=====→							X (ongoing related AEs, AESI, ongoing SAEs at EOT and new related AE/SAEs)	
Concomitant medication review	←=====→							X (related to AE/SAEs listed above)	From the date of informed consent form up to 30 days after the last dose of study treatment
Disease assessments:									
Disease recurrence assessment	X								At every visit and as clinically indicated until the detection of locoregional recurrence and distant recurrences (whichever comes last) or end of follow-up period, whichever comes first.

Procedure	Screening Period	Treatment Period [5 years – C1-C65]					EOT	Follow-up Period	Notes
		0	1	2	3	4-10 Q12 weeks			
Patient Visit #	Baseline	C1 D1	C2 D1	C4 D1	C7, C10, C13, C16, C19, C22, C25 D1	C28, C34, C40, C46, C52, C58 D1	D30 after last IMP dose	Q12 months after last IMP dose	
Patient Cycle Visit #	Up to 28 days before randomization	±3	±3	±7	±7	±7	±7	±45	
Time Window (day)									
Mammogram	X a				X b				
a. Screening: to be done if not already done in the past 6 months prior to randomization.
 
If local investigator plans to use MRIs instead of mammograms during the study, MRI will have to be performed at baseline
 
b. Post baseline: yearly from randomization (±30 days), and as clinically indicated until the detection of locoregional recurrence and distant recurrences (whichever comes last) or end of follow-up period, whichever comes first.

Procedure	Screening Period	Treatment Period [5 years – C1-C65]					EOT	Follow-up Period	Notes
		0	1	2	3	4-10 Q12 weeks			
Patient Visit #	Baseline	C1 D1	C2 D1	C4 D1	C7, C10, C13, C16, C19, C22, C25 D1	C28, C34, C40, C46, C52, C58 D1	D30 after last IMP dose	Q12 months after last IMP dose	
Patient Cycle Visit #	Up to 28 days before randomization	±3	±3	±7	±7	±7	±7	±45	
Time Window (day)									
Radionuclide Bone Scan Whole Body; CT Scan / MRI /PET-CT Ultrasound of Chest, Abdomen, Pelvis or any clinically indicated sites of disease; Clinical evaluation of superficial disease	(X a )				(X b )				
a. Screening: to be done for patients at highest clinical risk for disease recurrence as outlined in I 08 (Section 5.1), for patients with stage IIIA or higher as clinically indicated.
 
b. Post baseline: to be done as clinically indicated until the detection of locoregional recurrence and distant recurrences (whichever comes last) or end of follow-up period, whichever comes first.

Biopsy (disease recurrence proof)					(X)				Disease recurrence should be confirmed histologically whenever possible. For the locoregional recurrence including skin recurrence it is strongly recommended to perform a biopsy unless clinically contra-indicated.

Procedure	Screening Period	Treatment Period [5 years – C1-C65]					EOT	Follow-up Period	Notes
		0	1	2	3	4-10 Q12 weeks			
Patient Visit #	Baseline	C1 D1	C2 D1	C4 D1	C7, C10, C13, C16, C19, C22, C25 D1	C28, C34, C40, C46, C52, C58 D1	D30 after last IMP dose	Q12 months after last IMP dose	
Patient Cycle Visit #	Up to 28 days before randomization	±3	±3	±7	±7	±7	±7	±45	
Time Window (day)									
Overall Survival Follow-up								X	After discontinuation of study treatment, post-study survival status (including post-study anticancer therapies; disease recurrence for patients who complete or prematurely discontinue study treatment without disease recurrence) will be collected
Electronic PRO measures:									
EORTC QLQ-C30, EORTC QLQ-BR23, EORTC-QLQ-IL127, EQ-5D-5L, PGIS		X a					X b		a. Data collected prior to first IMP intake on device at site on D1 C1 or earlier if patient has no unrecovered acute toxic effects of prior AI therapy (see exclusion criteria 6). b. At each visit after the 1 st cycle (D1 C2-C58) during the treatment period, at EOT, and at the first two post-treatment follow up visits. Data collected on device at site.

Procedure	Screening Period	Treatment Period [5 years – C1-C65]					EOT	Follow-up Period	Notes
		0	1	2	3	4-10 Q12 weeks			
Patient Visit #	Baseline	C1 D1	C2 D1	C4 D1	C7, C10, C13, C16, C19, C22, C25 D1	C28, C34, C40, C46, C52, C58 D1	D30 after last IMP dose	Q12 months after last IMP dose	
Patient Cycle Visit #	Up to 28 days before randomization	±3	±3	±7	±7	±7	±7	±45	
Time Window (day)									
PGIC, MMAS-8					X				At each visit starting after the 1st cycle (D1 C2-C58) during the treatment period and at EOT. Data collected on device at site.
FACT-GP5, PRO-CTCAE items		X a				X b			a. Data collected prior to first IMP intake on device at site on D1 C1 or earlier if patient has no unrecovered acute toxic effects of prior AI therapy (see exclusion criteria 6). b. Data collected on device at home weekly in the first 6 weeks (+/-1 day) and every cycle on D1 C3-C6 (+/-7 days). Data collected on device at site at each visit starting after the 6 th cycle (D1 C7-C58) during the treatment period, at EOT, and at the first two post-treatment follow up visits.

Procedure	Screening Period	Treatment Period [5 years – C1-C65]					EOT	Follow-up Period	Notes
		0	1	2	3	4-10 Q12 weeks			
Patient Visit #	Baseline	C1 D1	C2 D1	C4 D1	C7, C10, C13, C16, C19, C22, C25 D1	C28, C34, C40, C46, C52, C58 D1	D30 after last IMP dose	Q12 months after last IMP dose	
Patient Cycle Visit #	Up to 28 days before randomization	±3	±3	±7	±7	±7	±7	±45	
Samples for Translational research:									
FFPE tumor tissue	X a						X b (optional)		Refer to Section 8.6.2 for details a. Most recent archived FFPE biopsied tumor tissue samples b. Collected at EOT for patients who discontinued treatment due to disease recurrence
Plasma biomarkers – Central labs		X a	X a				X b		Refer to Section 8.6.2 for details a. Pre-dose b. Collected at EOT for patients who discontinued treatment due to disease recurrence
Blood sample for genomic DNA – Central labs		X							Refer to Section 8.5 and Section 8.6.2 for details Pre-dose C1D1 after patient has discontinued AI
Blood sample for pharmacokinetics – Centralized assay			X a		X b				Refer to Section 8.4 and Section 8.6.2 for details a. At pre-dose b. Samples to be taken at pre-dose C7, C13 and C25

Procedure	Screening Period	Treatment Period [5 years – C1-C65]					EOT	Follow-up Period	Notes
		0	1	2	3	4-10 Q12 weeks			
Patient Visit #	Baseline	C1 D1	C2 D1	C4 D1	C7, C10, C13, C16, C19, C22, C25 D1	C28, C34, C40, C46, C52, C58 D1	D30 after last IMP dose	Q12 months after last IMP dose	
Patient Cycle Visit #	Up to 28 days before randomization	±3	±3	±7	±7	±7	±7	±45	
Time Window (day)		X a	X a				X b		Refer to Section 8.6.2 for details a. Pre-dose b. Collected at EOT for patients who discontinued treatment due to disease recurrence
(Optional) Blood Samples for Future Research									

All study visits performed during treatment period and follow-up period are conducted on-site (in participants without disease recurrence). On-site visits could be substituted by remote visits in specific circumstances.

**Screening:** Routine baseline tests performed prior to ICF signature do not need to be repeated as long as they are within the screening defined timeframe. Informed consent should be signed before any study specific procedures. It can be signed more than 28 days prior to randomization. Screening time indicates in which timeframe exams used to support eligibility have to be done prior to randomization.

**Randomization:** To take place once the consented patient has completed all the necessary screening procedures and is deemed eligible for study entry by the Investigator or designee. All eligible patients must be randomized using IRT. Every effort should be made to start treatment within 3 working days of randomization.

**Treatment period:** A cycle is defined as a 28-day period. Men and pre/perimenopausal women will receive GnRH analog on D1 of the cycle.

**Physical examination/ signs and symptoms evaluation:** At a minimum, assessments of the cardiovascular system, pulmonary system, gastrointestinal system (including palpation of liver and spleen), examination of the skin, and breast exam (palpation of breast/chest wall, axillae, supra- and infraclavicular regions). Symptom-directed physical examinations should be performed at screening and at each subsequent visit.

**Cycle 1 D1** refers to the day the patient receives the initial dose of IMP. Repeated evaluation of body weight, signs and symptoms, physical examination and laboratory tests is not necessary if performed within 7 days prior to 1st IMP administration. If evaluation performed during screening is abnormal, repeated evaluation is recommended within 2 days prior to 1st IMP administration.

**End of treatment (EOT):** should be performed 30 days (±7 days) after the last IMP and prior to the initiation of any new anti-cancer therapy, whichever comes first.

**Follow-up period:** each participant will be followed from EOT to up to 10 years from randomization except in case of premature study termination due to one of the following reasons: withdrawal of consent, loss to follow-up or death.

**PRO/HRQL assessments:** EORTC-QLQ-C30, EORTC-QLQ-BR23, EORTC-QLQ-IL127, FACT GP5, EQ-5D-5L, PRO-CTCAE, PGIC, PGIS, and MMAS-8 to be administered to each study participant after informed consent. At each assessment time, PRO/HRQL to be administered prior to any treatment- or study- related activities, including administration of IMP, laboratory work, radiological assessments, discussion with the participant regarding their treatment or health status, and similar activities

**Mammogram:** It shall not include patients with prior bilateral mastectomy. In case of unilateral mastectomy, unilateral mammogram will be performed.

Abbreviations: AE = adverse event; AESI = adverse event of special interest; AI = aromatase inhibitor; C = cycle; COA = clinical outcomes assessment; COD = cut-off date; CT scan = computed tomography scan; CTX = C-terminal telopeptide; DNA = deoxyribonucleic acid; D = day; DXA = Dual-energy X-ray absorptiometry; ECG = electrocardiogram; ECOG = Eastern Cooperative Oncology Group; EOT = end of treatment; EORTC = European Organization for Research and Treatment of Cancer; EQ-5D-5L = EuroQoL questionnaire with 5 dimensions and 5 levels per dimension; ER= estrogen receptor; FACT GP5 = Functional Assessment of Cancer Therapy – Item GP5; FFPE = formalin fixed paraffin embedded; FSH = follicle-stimulating hormone; GnRH= gonadotropin-releasing hormone; HRQL = health-related quality of life; IL127 = ad-hoc item list constructed from the EORTC item library; IMP = investigational medicinal product; IRT= interactive response technology; MRI = magnetic resonance imaging; MMAS = Morisky Medication Adherence Scale; NIMP = non-investigational medicinal product; PGIC = Patient Global Impression of Change scale- Side effects of treatment; PGIS = Patient Global Impression of Severity scale- Side effects of treatment; P1NP = Procollagen type I N-terminal propeptide; QLQ BR23 = EORTC QLQ breast cancer specific module; QLQ C30 = EORTC core quality of life questionnaire version 3; PRO = patient-reported outcome; PRO-CTCAE = patient-reported outcomes version of the common terminology criteria for adverse events; SAE = serious adverse event.

